The number of hospital readmissions (related to failure to thrive or cyanosis) may imply the overall clinical stability of a patient. Because these infants are at high risk for mortality at home, there are multiple reasons why they may be admitted to the hospital including clinically significant anemia which requires blood transfusions, poor weight gain, difficulty feeding, inadequate oxygen saturations, and illnesses. Each admission is stressful to the patient and their families. Having a normal hemoglobin level may have a role in preventing several of these factors, especially regarding failure to thrive or cyanosis.

D Investigational Agent

D1 Preclinical Data

Epoetin alfa is approved for use by the US Food and Drug Administration. The current labeled use is to treat a lower than normal number of red blood cells (anemia) caused by

chronic kidney disease in patients on dialysis to reduce or avoid the need for red blood cell transfusions. It should not be used in place of emergency treatment for anemia (red blood cell transfusions). It has not been proven to improve quality of life, fatigue, or well-being.

Common side effects include joint pain, muscle pain, bone pain, fever, cough, rash, nausea, vomiting, soreness of mouth, itching, headache, redness and pain in the injection site.

More serious side effects such as stroke, seizures, antibodies to Epoetin alfa, and serious allergic reactions have also been reported.

D2 Clinical Data to Date

There is no published clinical data on erythropoietin administration in the cyanotic congenital heart defect infant population that we are aware of.

D3 Claim for Exclusion of Environmental Assessment

In accordance with 21 CFR 25.31(e), I, [name] request a categorical exclusion from the requirement for an environmental assessment for the manufacture and formulation of *epoetin alfa* for use in human clinical trials under this IND #129795. All waste from the investigational drug will be properly controlled. The amount of wasted expected to enter the environment may reasonably be expected to be non-toxic. To my knowledge, no extraordinary circumstances exist.

D4 Dose Rationale and Risk/Benefits

500 units/kg/injection (SQ) and oral ferrous sulfate (iron) at 3 mg/kg/day (Donato 2005 & Maier 2002) which is an accepted treatment for anemia and prevention of anemia.

E Study Design

E1 Overview or Design Summary

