Epoetin alfa is a recombinant form of human erythropoietin used to stimulate erythropoiesis. Iron then helps support proper heme formation with the production of hemoglobin. EPO is administered by injections. Iron will be administered orally or intravenously if orals are not tolerated.

3.b Treatment Regimen

Experimental: Epoetin alfa and iron supplements:

Patients in the treatment group will receive weekly erythropoietin injections for 6 weeks starting before 8 weeks of age (at least one week after their surgery) at 500 units/kg/injection (SQ or IV).(Donato 2005 & Maier 2002) Oral ferrous sulfate 3 mg/kg/day of elemental iron will be given throughout the study if enteral feeds are tolerated which is an accepted treatment for anemia and prevention of anemia. If oral iron cannot be tolerated and there is laboratory evidence of iron deficiency, intravenous iron (either Iron sucrose or Iron dextran) will be used to replace iron stores based on the calculated iron deficit: Total replacement dose (mg of iron) = 0.6 x weight (kg) x [100 -

(actual Hgb /Desired Hgb x 100)]. This will be given in 5-7 mg/kg every day until the total replacement dose is achieved.

Iron studies (Serum iron, ferritin, total iron binding capacity) will be obtained at baseline and at week 14 with the final lab draw. If intravenous iron is used for replacement, iron studies will be repeated after replacement to ensure adequate iron stores.

All injections will be administered by a member of the subject's care team (bedside nurse, nurse practitioner, or physician) with a weekly visit in the cardiology clinic or in the hospital if the infant remains hospitalized after being dispensed by the research pharmacist.

A complete blood count will be obtained in the hospital prior to initiation of treatment for baseline measurements and to confirm eligibility if not obtained within 48 hours prior to the 1st injection as a part of the patient's standard of care. It will be repeated weekly (weeks 2-7) whether inpatient or outpatient, to confirm that there is no over-shoot with a hematocrit >45%. Labs will be reviewed prior to treatment. Treatment will be held for hematocrit levels >45%. There will be another lab drawn 14 weeks after the initial injection. Outpatient visits and lab draws will be paid for by the study grant. All labs will be analyzed by the Rady Children's Hospital Laboratory. The study drug will be provided by the study grant.

Observational Control:

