Screening for eligibility will be done on the Acute Cardiac Unit at Rady Children's Hospital. When an infant with cyanotic congenital heart disease is identified, the patient will be screened for eligibility based on the inclusion and exclusion criteria described above.

F2 Schedule of Measurements

The schedule of measurements is listed in Table 1 and Table 2. For the treatment arm, a physical exam with oxygen saturation will be recorded weekly from baseline and weeks 1-7, 14. A complete blood count will be drawn at baseline (if not already obtained for clinical use, one week post procedure and ≤ 48 hours prior to 1st injection), weekly from weeks 2-7, and at week 14. Iron studies will be drawn at baseline and week 14 unless indicated in between. All labs will be analyzed by the Rady Children's Hospital Clinical Laboratory whether inpatient or outpatient.

The control arm will have a physical exam with oxygen saturations at baseline, week 7 and 14. A complete blood count will be drawn at baseline (if not already obtained for clinical use, one week post procedure and ≤ 48 hours prior enrollment) week 7 and week 14. Iron studies will be drawn at baseline and week 14 unless indicated in between. All labs will be analyzed by the Rady Children's Hospital Clinical Laboratory whether inpatient or outpatient.

F3 Visit 1

Visit 1 will be prior to 8 weeks of age and at least 1 week post procedure while in the hospital. After confirmation of eligibility for the study, a physical exam and oxygen saturation will be obtained, and the 1st dose of the intervention will be given by the subject's care team if in the EPO arm.

F4 Visit 2 etc.

Visit 2-14 may either be obtained in the hospital or in the clinic setting. A physical exam and oxygen saturation will be obtained. A complete blood count will be obtained weekly from weeks 2-7 in the EPO arm. A complete blood count will be obtained in the control group at week 7 or earlier if indicated by the subject's care team. Study injections will be given after the lab has been reviewed and confirmed there is no overshoot (Hct >45%). There will be a final physical exam and labs at week 14 of the study, which will complete the participation of the study.

F5 Safety and Adverse Events

5.a Safety and Compliance Monitoring

Safety and Compliance Monitoring will follow standard principles as outlined below.

5.b Medical Monitoring

i Investigator

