G3 Analysis Plan

All primary analyses for efficacy will be performed on an intention-to-treat basis. All subjects will be analyzed according to their group assignment regardless of actual treatment received. In addition, both groups will be compared for safety at the end of the study by comparing adverse events and rates of adverse events. In the safety analysis, subjects will only be included if they actually received treatments in that group. (i.e. if a patient on the EPO arm did not get EPO, they should not be included in the analysis of safety in that arm).

G4 Statistical Methods

All data will only be gathered during the period in which the subjects will be active in the study (from baseline to 14 weeks post initial injection).

For the primary aim, we will compare the number of blood transfusions (one 10 ml/kg aliquot = 1 transfusion) between the two groups with a two-proportion z test. With $n = 20$ subjects per group, this test will have 80% power at the $\alpha = 0.05$ significance level to detect a difference. The primary aim will be assessed when all subjects have completed week 14.

We will compare weight gain and the change in oxygen saturation between baseline measurements and the 6 week follow-up with a two sample t-test. We will also use a linear mixed effects model, with a random intercept included to account for within subject correlation, to determine differences in the longitudinal trends in weight and oxygen saturation between groups. The length of the initial stay will be compared between groups with a two-sample t-test. We will treat the number of re-admissions (in regards to failure to thrive and cyanosis) as a categorical variable, and use Fisher's exact test to determine if there is a difference between EPO and control group readmission counts. We will consider the Mann-Whitney U test as a robust alternative to the two-sample t-test if the assumptions of the t-test are not met by the data.

With a sample size of $n = 20$ subjects per group, the t-tests described above will have 80% power at the $\alpha = 0.05$ level to detect an effect size equal to 0.91 times the common standard deviation. For weight change, assuming that the standard deviation of weights at baseline and the 6 week follow-up equal 1.22 and 1.53 (respectively), and assuming a

moderately high correlation between weight measurements within child of $\rho = 0.70$, this translates to a detectable difference of 1.00 kgs.

G5 Missing Outcome Data

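### The weight-trend model names only a random intercept; if infants grow at different rates, its group-by-time test is too liberal

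*Combined protocol and SAP*

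**What the plan says.** G4 plans two analyses of weight. The first is a two-sample t-test on the change from baseline to the 6-week follow-up. The second is a longitudinal model: "We will also use a linear mixed effects model, with a random intercept included to account for within subject correlation". Its purpose is "to determine differences in the longitudinal trends in weight and oxygen saturation between groups", which is a group-by-time contrast.

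G4 does not say how time enters the model, and it names no degrees-of-freedom method. It offers the Mann-Whitney test as a fallback for the t-tests but no fallback for the mixed model.

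The arms are examined on different schedules (F2, Tables 1 and 2). In the EPO arm the exam "will be recorded weekly from baseline and weeks 1-7, 14". For controls, "The control arm will have a physical exam with oxygen saturations at baseline, week 7 and 14". G4 sets the observation period as "from baseline to 14 weeks post initial injection". F6 lists weight among the outcomes without saying at which visits it is taken.

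**The concern.** A random intercept lets infants differ in level but not in growth rate, and it implies the same variance at every visit. When growth rates do differ, the model treats each infant's departure from the arm's average line as independent visit-to-visit noise. The slope contrast really rests on about 20 infants per arm, but the model credits every weight, so its standard error is too small.

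Two places in the documents make differing growth plausible. G4's own planning figures have the SD of weight rising from 1.22 kg at baseline to 1.53 kg at 6 weeks, which the named model cannot produce (rising residual variance could also explain it). C3 lists, among the reasons these infants may be admitted, "poor weight gain, difficulty feeding, inadequate oxygen saturations, and illnesses".

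What is at stake is a reported difference in weight trend that only reflects understated error. Weight gain is a declared secondary aim (C2). The point is limited to weight; no effect on saturation has been shown.

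**Working it through.** **The plan's own figure.** SD of change = sqrt(1.22² + 1.53² − 2 × 0.70 × 1.22 × 1.53) = 1.103 kg. With 20 per group, 80% power and a two-sided 5% t-test, the detectable effect is 0.909 SD, and 0.91 × 1.103 = 1.00 kg. G4's t-test figures reproduce. They do not bear on the mixed model, for which the plan gives no operating figure beyond the 5% level.

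**Inputs.**
- n = 20 per arm (G1, G4).
- Visit times in weeks from first injection (F2, Tables 1 and 2): EPO 0, 0, 1, 2, 3, 4, 5, 6, 14; control 0, 6, 14. The last visit is placed at 14 weeks, as G4 and section 3.b state ("There will be another lab drawn 14 weeks after the initial injection").
- Assumed: a weight at each scheduled exam, complete data, linear growth. The slope SD *a* and residual SD *e* are not in the documents and are varied.

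**Formulas.** Sxx is the sum of squared deviations of one infant's visit times: 150.9 for EPO and 98.7 for control. With *k* weights per infant:
- True variance of the slope difference = sum over arms of (a² + e²/Sxx)/n.
- Variance the random-intercept model reports = s² × sum of 1/(n Sxx), where s² = e² + a² × sum[(n−1)Sxx] / sum[(n−1) + n(k−2)].
- False-positive rate = 2 × P(Z > 1.96/sqrt(true/reported)).

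Here sum[(n−1)Sxx] = 19 × 249.6 = 4,742 and the divisor is (19 + 140) + (19 + 20) = 198. So s² = e² + 23.9 a².

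**One case in full:** a = 5 g/day = 0.035 kg/week, e = 0.2 kg.
- 1/150.9 + 1/98.7 = 0.01676.
- True variance = (2 × 0.001225 + 0.04 × 0.01676)/20 = 0.000156, so the SE is 1.78 g/day.
- s² = 0.04 + 0.0293 = 0.0693. Reported variance = 0.0693 × 0.01676/20 = 0.0000581, so the SE is 1.09 g/day.
- Ratio of variances 2.68; false-positive rate 23%.

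**False-positive rate (%) at nominal 5%:**

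| Slope SD, g/day | 0 | 1 | 2 | 3 | 5 | 7 |
|---|---|---|---|---|---|---|
| Scheduled visits, e = 0.1 kg | 5 | 10 | 19 | 26 | 32 | 35 |
| Scheduled visits, e = 0.2 kg | 5 | 6 | 10 | 15 | 23 | 28 |
| Scheduled visits, e = 0.3 kg | 5 | 6 | 7 | 10 | 16 | 22 |
| Shared visits only, e = 0.2 kg | 5 | 6 | 7 | 9 | 12 | 14 |

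Simulating the random-intercept REML fit at e = 0.2 kg (4,000 trials per setting, intercept SD 0.6 kg) gave 4, 7, 9, 15, 23 and 28%.

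**Limits.** As *e* goes to 0, the ratio on scheduled visits tends to 2/(23.9 × 0.01676) = 4.98, a rate of 38%. On the three shared visits it tends to 2.05, a rate of 17%. Placing the last visit at 13 weeks leaves both unchanged. With 30 per arm the worked case stays at 23%.

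**Two readings of the documents' own numbers.**
- If differing slopes explain G4's SDs and correlation, then a² = (1.103² − 2e²)/36. For e = 0.1 to 0.4 kg this gives slope SDs of 26 down to 23 g/day and false-positive rates of 38% down to 34% (simulation with baseline and week 1 merged: 32-36%).
- If C3's 15-30 g/day is read as mean ± 2 SD, the slope SD is 3.75 g/day. For e = 0.3 to 0.1 kg the rate is 12-29% on scheduled visits.

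**The case against.** The strongest reply is that little depends on this. G4 puts the t-test first and adds the mixed model to it; the t-test uses one change per infant and is valid whether or not growth rates differ. That stands and limits the weight of the point. The mixed model is, however, the only specified weight analysis that can use data after 6 weeks.

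Second, G4 names what is included and does not exclude a random slope. True, but an analyst following the text would fit the intercept alone. If a slope is intended, one sentence closes the matter.

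Third, the evidence for differing growth is indirect. C3 is a general rationale, and a baseline SD of 1.22 kg looks large beside birth-weight limits of 2.2-4 kg. That also stands: the table does not use G4's SDs, which would imply more slope variation than any column shows.

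Fourth, 38% is a limit only for the scheduled visits. Table 2 allows extra control exams at the care team's discretion; with nine weights in both arms the same formula tends to about 50%. If time were entered as a categorical visit effect, these percentages would not carry over directly.

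**Conclusion.** The concern holds as a conditional statement: with only a random intercept, the group-by-time test for weight is too liberal whenever growth rates differ between infants, and correct when they do not. On the scheduled visits the false-positive rate lies between 5% and 38%; on the shared visits alone it is at most 17%. Where it falls depends on slope variation relative to residual SD, which the documents do not give. At a slope SD of 1 g/day and residual SD of 0.2 kg it is only 6%.

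The figures assume linear growth, complete data and a weight at each scheduled exam. Informative dropout, non-linear growth and saturation were not tested. The plan should be changed, but no primary conclusion depends on it.

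**What to change.** State in G4 how time enters the model, and that for weight it has a random intercept and a random slope for time (unstructured 2×2 covariance) with a small-sample degrees-of-freedom correction such as Kenward-Roger.

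Name one fallback for a non-converged or boundary fit. It will be needed: at residual SD 0.2 kg, boundary fits occurred in 56, 34 and 7% of simulated trials at slope SDs of 0, 1 and 2 g/day. Two options work:
- a Welch t-test on per-infant least-squares slopes, which estimates the same slope difference and is the simpler choice;
- a repeated-measures model with unstructured covariance at baseline, week 7 and week 14.

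In simulation at the six slope SDs (residual SD 0.2 kg), false-positive rates were 3.7-6.1% for the random-slope model (1,000 trials each), 4.1-5.8% for Welch on slopes (4,000 each) and 4.3-5.8% for the unstructured model. Welch on slopes held 4.7-5.2% with 15% of post-baseline visits missing completely at random (2,000 trials).

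The cost is one or two sentences and no new data. At residual SD 0.2 kg the standard error of the trend difference becomes about 1.04, 1.06, 1.2 and 1.6 times larger at slope SDs of 0, 1, 2 and 5 g/day. Apart from the first, where it is a small price for the extra parameter, the widening mostly corrects the understated error.

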Children with cyanotic heart disease, “blue babies”, have chronically low oxygen levels and are at particular risk for death and poor outcomes because of their reduced ability to provide adequate oxygen to the body and brain. These infants should ideally maintain hemoglobin or red blood cell levels greater than 13 g/dL or a hematocrit >40% (Strauss 1991, Roseff 2002), to deliver adequate amounts of oxygen to the body. Healthy infants often experience a drop in their red blood cell level during their first few months of life, as part of the body's normal maturation process. Children with cyanotic heart disease experience this same phenomenon, but are also exposed to additional risks such as critical illness and surgical procedures. Thus, newborns with cyanotic heart disease may require blood transfusions as part of their care in order to provide adequate oxygen to the body. Although rare, the adverse outcomes due to transfusions can be devastating to this population. These complications include transmitted infections, transfusion reactions, additional hospitalizations, and production of antibodies that could complicate heart transplant if needed in the future. Epoetin alfa (EPO) and iron stimulate red blood cell production. Studies with EPO have been done in premature infants and children prior to surgery in order to assess the drug's ability to increase red blood cell levels [1-4]. They show that early administration of EPO has reduced the use of blood transfusions. We seek to investigate, through a prospective randomized controlled trial, if EPO and iron make a clinically significant difference in the number of transfusions given to infants with cyanotic heart disease. We hypothesize that prophylactic EPO and iron may prevent and/or decrease the amount of blood transfusions needed in this population.

A2 Primary Hypothesis

We hypothesize that prophylactic EPO and iron can prevent and/or decrease the amount of blood transfusions needed in this population.

A3 Purpose of the Study Protocol

The purpose of this study protocol is to provide a guide and timeline for the completion of this prospective randomized controlled trial.

B Background

B1 Prior Literature and Studies

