There are centers in the United States that have developed protocols using erythropoietin to minimize blood product transfusions before and after surgery, also referred to as "bloodless surgery"[4]. There have been retrospective studies evaluating the success of these protocols, but there are no randomized controlled prospective studies that have studied the effects of erythropoietin in patients with cyanotic heart disease in regards to transfusion prevention. There have also been multiple studies looking at the efficacy of EPO in the premature infant population (Donato 2005). In these studies, EPO has been shown to prevent blood transfusions. However, these findings did not represent a clinically significant difference for the study population in the long term. The clinical significance is enhanced in our study population, because blood transfusions may have significant implications for transplant candidacy in the future and transplant complications if needed. Last, there is a study involving infants and children with craniosynostosis showing that EPO is safe and can reduce the number of blood transfusions in a surgical group that has high risk for bleeding (Fearon 2001).

C Study Objectives

C1 Primary Aim

Congenital cyanotic cardiac patients require higher hemoglobin concentrations for optimal oxygen delivery. Prophylactic erythropoietin can prevent and/or decrease the amount of blood transfusions needed prior to surgery. We seek to investigate if erythropoietin makes a clinically significant difference in the number of transfusions given to these patients and the morbidity associated with it during the period in which the subjects will be active in the study (from baseline to 14 weeks post initial injection). The primary aim will be assessed when all subjects have completed week 14 or discontinued early.

C2 Secondary Aim

We will also look to see if administering erythropoietin makes a clinical significance in the following outcomes during the period in which the subjects will be active in the study

(from baseline to 14 weeks post initial injection): weight gain, oxygen saturations, length of initial hospital stay, and hospital readmissions (related to failure to thrive or cyanosis).

C3 Rationale for the Selection of Outcome Measures

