Transfusions are currently the treatment of choice for clinically significant anemia in the cyanotic congenital heart patient. However, this therapy requires hospitalization and an intravenous line which does not come without risk, in addition to the risks associated with transfusions which include transfusion reactions from blood type incompatibility, antibody sensitization, and infections. Thus, the primary outcome will be to see if the number of transfusions can be reduced by administering erythropoietin.

Although the hemoglobin level, in and of itself, should not affect oxygen saturation measured by pulse oximetry, our anecdotal experience suggest that oxygen saturations in patients with cyanotic heart disease frequently improve after a blood transfusion to increase the amount of hemoglobin. Thus, the secondary outcome of oxygen saturation will be looked at for 2 reasons. First, to ensure that the treatment and control arms are similar at baseline to prevent bias for transfusions based on criteria set below. Second, to determine if our anecdotal experience has any validity.

The secondary outcome of weight gain is appropriate in the setting of infants as this variable has been used to monitor the ability to thrive and meet the body's metabolic demands. It is well established in pediatrics that the neonate and infant should gain 15-30 grams per day for optimal growth. Infants who are cyanotic, already have a deficiency in meeting their metabolic demands due to a reduced oxygen carrying capacity. This is further complicated in the instance of anemia. Thus, infants may have an increased ability to optimize weight gain in the setting of normal, stable hemoglobin levels which may be achieved with erythropoietin.

Often, cyanotic congenital heart defect neonates have prolonged initial hospital stays due to the inability to maintain acceptable oxygen saturations, and transition to adequate oral intake for appropriate weight gain. If the hospital stay is found to be shortened after starting erythropoietin, this may be of clinical and financial significance.

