The study will be a prospective randomized controlled trial, to investigate if administration of EPO and supplemental iron make a clinically significant difference in the number of transfusions given and the morbidity associated with it in infants with cyanotic heart disease. There will be 2 arms in the study, a treatment arm (EPO) and an observational control arm. The patients will be enrolled in the neonatal period after diagnosis and initial palliative procedure (surgical shunt, hybrid procedure, stent in patent ductus arteriosus or right ventricular outflow tract to ensure adequate pulmonary blood flow). They will be followed for 14 weeks from their enrollment. Clinical data will be obtained as appropriate to study the primary and secondary outcomes. The data will be analyzed with a biostatistician to reveal any statistically significant differences between the 2 arms of the study.

E2 Subject Selection and Withdrawal

2.a Inclusion Criteria

- Newborns less than 4 weeks old at diagnosis
- Gestational age ≥ 34 weeks
- Birth weight 2.2-4kg
- Infants with cyanotic heart disease who have had a surgical aorto-pulmonary shunt, hybrid procedure (pulmonary artery bands with a patent ductus arteriosus stent or PGE-1 to maintain ductal patency) or a catheterization intervention that is equivalent to a shunt (patent ductus arteriosus stent, right ventricular outflow tract stent).
- Baseline hematocrit to be below $<40\%$.
- Completes at least 1 injection in the study by 8 weeks of age.

2.a Exclusion Criteria

- Infants diagnosed at greater than 4 weeks of age
- Gestation <34 weeks
- Birth weight <2.2 kg or >4 kg
- Hematocrit $>40\%$
- Newborns with acyanotic heart disease
- Infants with significant co-morbidities
 - Renal failure (Creatinine > 2 standard deviations above age adjusted norm)
 - Hepatic failure (elevated AST/ALT levels > 2 standard deviations above age adjusted norm)
 - Hemolytic disease
 - Hemoglobinopathies (Sickle-cell disease, Thalassemias)

2.b Ethical Considerations

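### Length of initial stay has no rule for infants who die in hospital or are still in hospital at week 14, and neither the t-test nor its fallback supplies one

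*Combined protocol and SAP*

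**What the plan says.** Length of initial stay is a secondary outcome. Section C2 gives the window and the outcomes together: "from baseline to 14 weeks post initial injection): weight gain, oxygen saturations, length of initial hospital stay". Section G4 applies the same limit to everything: "All data will only be gathered during the period in which the subjects will be active in the study". The design summary in E1 starts the clock at a different point: "They will be followed for 14 weeks from their enrollment".

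The test in G4 is: "The length of the initial stay will be compared between groups with a two-sample t-test". The fallback is conditional: "We will consider the Mann-Whitney U test as a robust alternative to the two-sample t-test if the assumptions of the t-test are not met".

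Section C3 treats a shorter stay as a possible clinical and financial benefit, so fewer days count in favour of an arm.

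Both difficult cases are foreseeable. C3 says that these "neonates have prolonged initial hospital stays due to the inability to maintain acceptable oxygen saturations", and the abstract says that such children "are at particular risk for death and poor outcomes". Infants are inpatients when treatment starts (F3): "Visit 1 will be prior to 8 weeks of age and at least 1 week post procedure while in the hospital".

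Section G5 is the only missing-data rule. It scores a missing outcome as a transfusion and allows an optional completers analysis. Neither tells the analyst how many days to enter for a death or an open stay. The intention-to-treat statement in G3 covers the primary efficacy analyses. No section defines when the initial stay begins or ends.

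**The concern.** A number of days in hospital shows benefit only if it ends in discharge alive. For an infant who dies on the ward, the observed days stop at death, and a direct calculation enters a low number. An arm with more in-hospital deaths then looks better on an outcome where low is good. Section F5 lists strokes and clotting events among the expected events with the study drug, so a harm could register as a gain. If deaths are set to missing instead, the comparison is restricted to survivors.

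An infant still in hospital when data collection stops has a stay known only to exceed the observed value. Entering that value caps the longest stays, and leaving the infant out removes them.

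The plan does not choose among these options, and they give different answers. The trial is unblinded (E2 2.d, E3 3.h), so the choice should not wait until the data are known.

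**Working it through.** **The plan's own figure.** G4 gives the t-tests 80% power at 0.91 SD with 20 per group. The noncentral t (38 df, two-sided 0.05) gives 80.1%, so the figure reproduces. It presumes a complete, roughly normal outcome and does not bear on deaths or open stays.

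**Inputs.** From the documents: 20 per arm (G1) and a window of 14 × 7 = 98 days (C2, G4). The documents give no stay distribution, SD or in-hospital death rate, so the following are assumptions:
- Stay after baseline is log-normal with median *m* = 30, 45 or 60 days and log-SD *s* = 0.8.
- Death falls uniformly within the stay.
- Deaths are 5% in one arm and 15% or 25% in the other.

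**Deaths, no true effect, m = 30.**
- Uncapped mean: 30 × exp(0.8²/2) = 41.3 days.
- With k = ln(98/30)/0.8 = 1.48, the capped mean is 41.3 × Φ(k − 0.8) + 98 × (1 − Φ(k)) = 41.3 × 0.752 + 98 × 0.069 = 37.9 days.
- A death at a uniform point loses half of this on average, so the bias is 0.5 × 37.9 × (difference in death proportion).
- 5% v 15%: 0.5 × 37.9 × 0.10 = 1.9 days shorter for the arm with more deaths.
- 5% v 25%: 0.5 × 37.9 × 0.20 = 3.8 days shorter.
- The SD of capped stay is about 26 days, so the standard error of the difference is about 26 × √(2/20) = 8 days.
- Simulated t-test rejection, nominally 5%, is about 5.6% and 7.4%.

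The convention for deaths decides the direction. For 5% v 15%, ending the stay at death gives −1.9 days and excluding deaths gives about 0. Giving each death the full 98 days gives (98 − 37.9) × 0.10 = +6.0 days.

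**Open stays, no deaths, a true 40% shortening.**

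| Control median (days) | Controls past day 98 | True mean difference | Difference if capped at 98 | Difference if open stays dropped |
|---|---|---|---|---|
| 30 | 7% | 16.5 | 13.7 | 10.5 |
| 45 | 17% | 24.8 | 16.8 | 11.1 |
| 60 | 27% | 33.1 | 17.9 | 10.8 |

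The reported difference in days is therefore too small. Power is a separate matter. With 20 per arm, t-test power is about 40% on uncapped stays and about 45% to 47% on capped ones, because the cap shrinks the variance by more than it shrinks the difference. Mann-Whitney power is about 47% with or without the cap, since capped stays become ties at the top. Ranks do nothing for deaths, because an early death still ranks among the shortest stays.

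**The case against.** Four stronger readings are tempting, and the documents do not support them.

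- **The plan scores a death as an early discharge.** It does not say so. It is silent, and a death could equally be set to missing or left out of the completers analysis. The gap is the missing rule.
- **Any stay over 14 weeks is cut off.** The limit runs from the first injection (C2, G4) or enrollment (E1), and Visit 1 is at least a week after the procedure. A stay counted from admission can exceed 14 weeks and still be observed in full.
- **The cap costs power.** The working shows that it does not. What suffers is the estimate in days.
- **The protocol predicts high in-hospital mortality.** Its remarks on death are general, and the specific one in C3 concerns mortality at home. No in-hospital rate is given.

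It can also be said that the death bias is small against its standard error and needs a three- to five-fold excess of deaths. The DSMB meetings (F5 5.b), the interim safety review (G2) and the final adverse-event comparison (G3) should reveal such an excess. Ranking death worst is also one of several defensible choices, alongside competing-risk time to discharge or days alive and out of hospital.

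All of this limits the size of the point and stands. It does not supply the missing rule. Safety monitoring would not correct a published difference in stay that favours the arm with more deaths.

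**Conclusion.** The gap is real, modest in size and cheap to close. The plan names a test for length of initial stay but gives no rule for in-hospital death or for infants still in hospital at week 14. Direct use of observed days would score a death as a short stay or lose it, and would understate the mean difference in days through the cap. Mann-Whitney resolves the cap only.

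On the assumed inputs, a 10- or 20-point excess of in-hospital deaths makes that arm look about 2 or 4 days shorter, with a standard error of about 8 days and little inflation of the false-positive rate. These sizes depend on an assumed stay distribution and assumed death rates. The absence of a rule does not depend on them. The outcome is secondary, and the primary transfusion analysis is unaffected.

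**What to change.** In G4, replace the t-test for this outcome with the following:

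1. Count the stay from randomization (or baseline) in both arms. Days before that cannot reflect treatment, and control infants have no first injection to count from.
2. Use one pre-specified Wilcoxon rank-sum test on this order: discharged alive, by day of discharge; then still in hospital at week 14, all tied; then died before discharge, as the worst outcome.
3. Show cumulative discharge-alive curves by arm with death as a competing event, and report deaths by arm beside the result.

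The cost is mainly wording. F6 already lists hospitalizations and adverse events, but the form pages available do not show whether discharge and death dates are recorded, so this should be confirmed. The downside is that the result is no longer a simple difference in mean days, and the test reflects mortality as well as stay. For that reason the deaths and the curves should be shown with it.
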